
Study Populations:
	
The following three analysis populations are planned for this study:
 
 
• The Safety Population will include all subjects who received any part of a dose of study treatment.
 
• The PK Population will include all subjects who receive a full dose of study treatment and complete all PK assessments through the T6h timepoint.
 

	
Subjects who fail to complete these PK assessments will be replaced.
 

• The intent-to-treat (ITT) population will include all subjects as randomized to study treatment. The modified intent-to-treat (mITT) Population will include all subjects who receive a full dose of study treatment and complete the first 3 pain assessments (through T2h).

• Inpatient study completers (Inpatient Completers) will include all subjects who receive a full dose of study treatment and complete the inpatient assessment period (through T96h).

• Study completers (Study Completers) will include all subjects who receive a full dose of study treatment and complete the entire study period through D29±2/W4.

 
Subjects who elect to discontinue study participation during the inpatient phase of the study, will be asked to continue with assessments through T96h if they have not elected to withdraw from all aspects of study participation. Subjects who elect to discontinue participation prior to D8 (W1) will be considered to have terminated as of the date of their election, however they will be asked to return to the site one time, if willing and at their convenience, to ensure wound healing.
 
All safety assessments and baseline characteristics will be summarized using the Safety Population. PK and efficacy analyses will be performed using the PK and mITT Populations, respectively. Additional efficacy analyses will be performed on the ITT, Inpatient Completer and Study Completer Populations. All summaries will be grouped by the actual treatment received. Each active dose cohort will be presented separately, along with a combined active dose group.

--	---

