
Multimodal Analgesia and Rescue Medication during Outpatient Period:
	
Once discharged from the inpatient unit, all study participants will be instructed to take a combination of OTC analgesics (NSAID and acetaminophen) at an appropriate dose per medical judgment to manage any residual or breakthrough postsurgical pain through D29/W4. Administration of rescue medication should be based on T0.
 
Outpatient period: D4 through D29/W4, if needed for pain management, the following oral over-the-counter (OTC) analgesics will be recommended for subjects to self-administer (note that these medications will not be provided by the sponsor):
 
 
• NSAID (e.g., ibuprofen 200 – 400 mg prn up to qid [Advil® or Motrin®] or naproxen 220 mg prn up to tid [Aleve®]) or other options per investigator discretion and
 
• Acetaminophen 1-2 500 mg tablets prn up to tid or 650 mg prn up to qid (3g daily maximum limit)
 
 
If a subject is still requiring opioid rescue in the 12h prior to discharge from the inpatient unit (i.e., from T84h on regardless of whether discharge is delayed), then prescribe no more than 6 tablets (1 PO tid prn) of oxycodone 5 mg for the initial outpatient period with the number of tablets dispensed and refills as needed per investigator discretion.
 
Persistent pain or pain exacerbations during the outpatient period may suggest the need for an unscheduled in-person visit to assess the surgical site. If such a situation occurs, the Investigator should use clinical discretion on adequacy of analgesic treatment, but to capture this event as an adverse event (AE) and document any required treatments.

Inclusion Criteria:
	
In order to participate, subjects must meet all inclusion criteria:
 
 
1. In the medical judgment of the investigator, be a reasonably healthy adult aged 18 - 75 years old, inclusive, and American Society of Anesthesiology (ASA) physical Class 1, 2 or 3 at the time of randomization (Appendix 1A).
 
2. Plan to undergo an elective primary unilateral first metatarsal Bunionectomy repair, without collateral procedure or additional surgeries, to be performed under light to moderate sedation with regional anesthesia.
 

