
Other Endpoints:
	
 
● <math>AUC_{0\text{ to }24h}</math>, <math>AUC_{0\text{ to }120h}</math>, <math>AUC_{0\text{ to }W1}</math> (walking), <math>AUC_{0\text{ to }W2}</math>, <math>AUC_{0\text{ to }W2}</math> (walking), <math>AUC_{12\text{ to }24h}</math>, <math>AUC_{24\text{ to }48h}</math>, <math>AUC_{24\text{ to }72h}</math>, <math>AUC_{24\text{ to }96h}</math>, <math>AUC_{96h\text{ to }120h}</math>, <math>AUC_{96h\text{ to }W1}</math>, <math>AUC_{24h\text{ to }W1}</math>(walking), <math>AUC_{96h\text{ to }W2}</math>, <math>AUC_{96h\text{ to }W2}</math>(walking)
 
● <math>OC_{24\text{ to }48h}</math>, <math>OC_{24\text{ to }72h}</math>, <math>OC_{24\text{ to }96h}</math>
 

	
 
• OF24 to 96h, OF96h to W1 and OF96h to W2
 
• TTFRafter T0 and TTFRafter T24h
 
• Analgesic consumption from T96h to W1 (AC96h to W1) and AC96h to W2
 
• PGE comparing the %age of subjects reporting “poor” + “fair” vs. “good” + “excellent” responses, and the %age reporting each category of response at W1, W2 and W4
 
• IGE comparing the %age of those reporting “poor” + “fair” vs. “good” + “excellent” responses, and the %age reporting each category at W1, W2 and W4
 
• Number and %age subjects with an AE of lack of efficacy (LOE) during the inpatient period: LOE0 to 96h
 
• HCU96h to W2 and HCU96h to W4
 

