Safety Endpoints:	
The following safety endpoints will be evaluated:
 
 
• Incidence of TEAEs or treatment-emergent SAEs from D0/T0 through D29: Note that all AEs will be recorded from the time the informed consent form (ICF) is signed through D29 (or D36 as applicable). TEAEs are defined as AEs occurring post T0 (end of study treatment infiltration).
 
• Surgical site assessment / wound evaluations to assess for atypical skin reactions, e.g., erythema, pain, pruritus, bruising, swelling, bruising or other skin changes, should be evaluated and graded for severity and followed regularly until resolution or a stable baseline is achieved.
 
• Physical examination (PE) of the lower extremities and vital signs, including neurosensory testing of both lower extremities 
 
○ Note that any observed or reported sensory deficit or clinically significant persistent sensory change remote from the immediate surgical site, such as allodynia or hyperalgesia, must be designated as a neurologic AE. Subjects should be followed until resolution or a stable baseline is achieved.
 
○ Numbness proximal to the incision need not be considered a neurologic AE since this could occur because of tissue trauma and inflammation from the surgery.
 
 
 
• ECG changes from screening to T24h post-treatment
 
• Clinically significant clinical labs changes from screening
 

Pharmacokinetics:	
Approximately 1/3rd of enrolled subjects at each site will participate in the PK study (48 in total; 12 in each treatment group). The PK population will include all subjects who have sufficient concentration-time profiles for estimation of PK parameters.
 
Based upon the PK results from the Phase 1 bunionectomy ascending dose safety study, the time points for whole blood collection will be at baseline (within the 30 min before the start of study treatment dosing), and T5min, T10 min, T15min,

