### 11.2.3. Outpatient Analgesic Medications

Once discharged from the inpatient unit, all study participants will be instructed to take a combination of OTC analgesics (NSAID and acetaminophen) at an appropriate dose per medical judgment to manage any residual or breakthrough postsurgical pain through D29/W4.

Outpatient period: T96h through D29/W4:

- If needed for pain management, over-the-counter (OTC) analgesics administered PO, e.g.,
  - NSAID (e.g., ibuprofen 200 mg to 400 mg prn qid [Advil® or Motrin®] or naproxen 220 mg prn tid [Aleve®])
  - Acetaminophen 1-2, 500 mg tablets (up to 1 g) tid or 650 mg qid (3g daily limit)

If a subject is still requiring opioid rescue in the period beyond the T84 hour timepoint, then prescribe no more than 6 tablet supply of oxycodone 5 mg (for use up to tid prn) to cover the initial outpatient period with actual number of tablets prescribed and refills per investigator discretion and based upon the subject's needs.

Persistent pain or pain exacerbations during this period may suggest the need for an unscheduled in-person visit to assess the surgical site. If such a situation occurs, the Investigator should use clinical discretion on adequacy of analgesic treatment, but capture this event as an AE and document any required treatments.

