#### 12.6.1.3. Other Efficacy Endpoints

- $AUC_{0\text{ to }24h}$ ,  $AUC_{0\text{ to }120h}$ ,  $AUC_{0\text{ to }W1}$  (walking),  $AUC_{12\text{ to }24h}$ ,  $AUC_{24\text{ to }48h}$ ,  $AUC_{24\text{ to }72h}$ ,  $AUC_{24\text{ to }96h}$ ,  $AUC_{96h\text{ to }120h}$ ,  $AUC_{96h\text{ to }W1}$ ,  $AUC_{24h\text{ to }W1}$ (walking),  $AUC_{96h\text{ to }W2}$ ,  $AUC_{96h\text{ to }W2}$ (walking)
- $OC_{24\text{ to }48h}$ ,  $OC_{24\text{ to }72h}$ ,  $OC_{24\text{ to }96h}$

- OF24 to 96h, OF96h to W1 and OF96h to W2
- TTFRafter T0 and TTFRafter T24h
- Analgesic consumption of OTC analgesics and if prescribed, oxycodone, from T96h to W1 and T96h to W2
- PGE comparing the %age of subjects reporting “poor” + “fair” vs. “good” + “excellent” responses, and the %age reporting each category of response at W1, W2 and W4
- IGE comparing the %age of those reporting “poor” + “fair” vs. “good” + “excellent” responses, and the %age reporting each category at W1, W2 and W4
- Number and %age Subjects with an AE of lack of efficacy (LOE) during the inpatient period: LOE24 to 96h, LOE0 to 96h
- HCU96h to W2 and HCU96h to W4

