8.2 Adverse Events

Any untoward medical event that occurs after signing the informed consent form (ICF) is considered to be an adverse event (AE). All AEs will be recorded through 29 days (or 36 days as applicable) or ET, after the completion of surgery. SAEs will be recorded until 30 days after the 29 day follow up visit or ET, whichever occurs earlier. Treatment-emergent AEs are defined as AEs that start or worsen in severity after the end of study treatment infiltration (post T0). Verbatim terms used by investigators to identify AEs in the CRFs will be mapped to the appropriate preferred term (PT) and system organ class (SOC) using a standardized coding dictionary (MedDRA Version 21.0). All coding will be reviewed prior to database lock. All recorded AEs will be listed, but only TEAEs will be summarized.

For evaluation of causal relatedness to treatment, the categories are probably related, possibly related or unlikely related. For categorization in the summary tables, AEs designated as probably or possibly related will be considered to be related.

For the evaluation of event severity terms, the criteria are mild, moderate, severe or potentially life-threatening.

In addition to a listing of all TEAEs, treatment related TEAEs, serious TEAEs, Deaths, and TEAEs leading to premature discontinuation from the study will be provided.

An overall summary will be prepared giving for each treatment group and overall both the number of TEAEs, and the number of subjects with at least one TEAEs, as well as SAEs, treatment related TEAEs and TEAEs leading to premature discontinuation from study.

The number of subjects with AEs will be summarized for each treatment group by SOC and PT sorted in alphabetically by SOC, and then by PT within SOC. These summaries will be given by treatment in separate tables for each of the following TEAE event sets:

- All events
- Treatment related events
- Serious events
- Events leading to premature discontinuation from study
- Events by maximum severity

If a given subject experiences a TEAE that maps to the same PT/SOC more than once, the subject will be counted only once for the SOC/PT at the greatest severity (i.e., mild, moderate, or severe) and causality (i.e., attribution to study material).

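### Pain and lack-of-efficacy events that reach the AE page enter the pooled TEAE counts, so better analgesia on CA-008 could dilute an excess of other TEAEs in those counts

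*Protocol*

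**What the plan says.** **LOE as an AE.** The protocol synopsis (Other Endpoints) has "Number and %age subjects with an AE of lack of efficacy (LOE) during the inpatient period". Protocol 12.6.1.3 repeats this and adds the 24 to 96 h period.

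**Outpatient pain as an AE.** For persistent pain or exacerbations after discharge, which may call for an unscheduled visit, the synopsis tells the investigator to "capture this event as an adverse event (AE) and document any required treatments". Protocol 9.1.4 and 11.2.3 say the same.

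**LOE apart from AEs.** SAP 7.4.3 and 7.5.7 define the inpatient LOE endpoint as dropout due to an AE or LOE, read from the end-of-study page of the eCRF. SAP 7.5.5 also uses LOE as a discontinuation reason.

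**What is counted.** The first-listed safety endpoint in the synopsis is "Incidence of TEAEs or treatment-emergent SAEs from D0/T0 through D29". The synopsis and SAP 8.2 place TEAEs after T0, and SAP 8.2 adds worsening. Protocol 15.7.1 words the window differently. None of the three excludes LOE or pain. The SAP 8.2 overall summary gives, for each group, "both the number of TEAEs, and the number of subjects with at least one TEAEs", with further totals for serious events, related events and events leading to discontinuation. Related events and maximum severity are also tabulated by SOC and preferred term (Tables 14.3.1.3 and 14.3.1.6).

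The protocol does exempt numbness near the incision from AE reporting. It has no matching rule for expected surgical pain.

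**The concern.** Poor pain control is the outcome CA-008 is meant to change. If it is also counted as a harm, the any-TEAE comparison carries some of the efficacy result. Protocol 15.6 expects more rescue use on placebo, which makes it plausible, though not certain, that pain and LOE events will be commoner there. The pooled comparison would then lean towards making the drug look safe, and more so the better it works.

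Safety against placebo is a stated secondary objective. Protocol 15.7 plans no formal safety tests, so the descriptive tables carry that comparison. The count that would separate the two components, subjects with at least one TEAE other than pain or LOE, is not planned.

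**Working it through.** **Plan's own figures.** Protocol Table 2 gives Phase 1 TEAE rates of 16/29 = 55.2% on all active doses and 4/8 = 50.0% on placebo, a gap of 5.2 points. Both reproduce. The by-subject Phase 1 listing was not in the text available, so whether these rates already include pain events cannot be checked.

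**Model.** Let p be the proportion of subjects with at least one other TEAE and q the proportion with a pain or LOE AE. If the two are independent within an arm,

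any-TEAE rate = 1 − (1 − p)(1 − q).

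**Inputs.** Placebo p = 50% is the Phase 1 rate. Active p = 60%, a true 10-point excess, is assumed. All q values are assumed, because neither document gives one.

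Active, q = 5%: 1 − 0.40 × 0.95 = 62.0%.

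| Placebo q | Placebo any-TEAE rate | Apparent excess (true: 10 points) |
|---|---|---|
| 10% | 1 − 0.50 × 0.90 = 55.0% | 7.0 points |
| 15% | 1 − 0.50 × 0.85 = 57.5% | 4.5 points |
| 24% | 1 − 0.50 × 0.76 = 62.0% | 0 points |

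**Break-even.** The placebo q that cancels the excess is 1 − (1 − p_active)(1 − q_active)/(1 − p_placebo). With q_active = 5%:

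- 10-point excess: 1 − 0.40 × 0.95/0.50 = 24%
- 15-point excess: 1 − 0.35 × 0.95/0.50 = 33.5%
- 20-point excess: 1 − 0.30 × 0.95/0.50 = 43%
- Gap of the Phase 1 size (55.2% vs 50.0%): 1 − 0.448 × 0.95/0.50 = 14.9%. With no such AEs on active it is 1 − 0.448/0.50 = 10.4%.

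**Dependence on overlap.** Take q = 5% active and 15% placebo. If pain/LOE AEs occur only in subjects who already have another TEAE, the rates stay at 60% and 50% and nothing is lost. Under independence the excess is 4.5 points. With no overlap, both arms show 65% (60 + 5 and 50 + 15) and the excess is 0.

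**Why the term rows do not give the missing count.** Suppose the any-TEAE rate and the flagged-event rate are both known. The rate of other TEAEs then lies only between their difference and the any-TEAE rate. In the 15% case that is 57.0% to 62.0% on active and 42.5% to 57.5% on placebo. The excess could be anywhere from 57.0 − 57.5 = −0.5 to 62.0 − 42.5 = 19.5 points. Adding the other preferred-term rows does not settle it, because one subject can appear under several terms.

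**The case against.** **Inpatient LOE may never reach the AE page.** The AE reporting section (protocol 13.1.2) does not name it, and the SAP takes it from the end-of-study page. This stands. A reader might infer from the endpoint's name that LOE is certain to be in the TEAE rate, but the documents leave that open. The outpatient pain instruction is unaffected.

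**Outpatient pain that may prompt a wound check is a legitimate safety event.** This stands too, and it is a reason to add a count rather than remove one. Protocol 7.1.4 also expects transient hyperalgesia and burning from TRPV1 agonists, so some pain AEs on CA-008 may be drug harm.

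**The tables already separate terms.** This largely stands. It is tempting to say that the plan offers no split and could conceal harm altogether. However, the related and severity tables are by SOC and preferred term, and wound and neurosensory findings have their own summaries. Greatest severity is taken within SOC and preferred term, so a severe pain event cannot mask the severity of a different term. Only the pooled subject counts are affected.

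**No conclusion could rest on 10 points.** At 36 per arm the standard error of 60% versus 50% is √(0.60 × 0.40/36 + 0.50 × 0.50/36), about 12 points. That limits what the line can show, but does not justify a systematic lean in it.

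**The count can be rebuilt from the AE listing.** It can, but SAP section 10 would then label it post hoc, with terms chosen after treatment is known.

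**Conclusion.** The point holds for the pooled subject-level counts, chiefly the any-TEAE line of Table 14.3.1.1. Pain or LOE events on the AE page after T0 are counted there with all other harms, no count without them is planned, and the two documents disagree on how LOE is classified.

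The size is unknown. Under the assumed rates and independence, a 10-point excess shrinks to between 7.0 and 0 points as the placebo pain/LOE rate rises from 10% to 24%. Larger excesses need 33.5% to 43% on placebo to vanish, so dilution is more likely than full concealment. The effect shrinks further if these events occur mainly in subjects with other TEAEs, and grows if they do not.

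A reader might go further and conclude that the placebo rate will be inflated. The documents support only that it can be: they expect more rescue use on placebo, rescue use is not itself an AE, and no LOE or pain-AE rate is stated. This is an inexpensive improvement to a descriptive summary, not a flaw in the safety evaluation as a whole.

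**What to change.** 1. Reconcile the protocol (synopsis and 12.6.1.3) with SAP 7.4.3, 7.5.5 and 7.5.7, stating whether LOE is recorded as an AE, as a discontinuation reason, or as both.
2. In SAP 8.2, define a flag for AE terms of LOE or pain at the operated foot, set by blinded review before unblinding.
3. In Table 14.3.1.1, and in any any-event total line of Tables 14.3.1.3 and 14.3.1.6, add a row for subjects with at least one TEAE excluding flagged events.
4. Keep every all-TEAE row. Capsaicin can itself cause hyperalgesia and burning, so the excluding row must be read beside the full count and not replace it.

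The cost is one flag variable, a short blinded review of AE terms and one extra row per table. It needs no new data and no change to clinical procedures.

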#### 4. TABLE 1. SCHEDULE OF ASSESSMENTS

Assessment	Screening	In Patient							Follow-Up				Unscheduled Visit	Early Termination
		Prior to Surgery	Surgery	Post-Surgery	24h	48h	72h	96h	8±1 days	15±2 days	29±2 days	36±2 days 		
Study Day	-45 to -1	0	0	0	1	2	3	4						
Informed Consent	X	X												
Screening Medical and Surgical History	X	X												
Inclusion/Exclusion Criteria	X	X												
Screens for alcohol/drugs of abuse	X	X												
Enroll/Randomize		X												
Demographics	X													
Subject Pain Assessment Training	X													
Surgery			X											
Study treatment Infiltration/institution			X											
Pregnancy Test	X  (serum)	X  (urine)												
Vital Signs	X	X		X 	X 	X 	X 	X 	X	X	X			X
Physical Examination 	X 	X 						X 	X 	X 	X 			X
12-Lead ECG	X				X 									
Surgical Site assessment								X 	X	X	X	X	X	X
Neurosensory Exam	X							X 	X	X	X	X	X	X
Blood draw for hematology and serum chemistry	X	X 						X 						
Urine sample for urinalysis	X	X						X 						
X-ray of surgical site	X										X			X
Concomitant Medication Assessment	X	X		X	X	X	X	X	X	X	X	X	X	X
Adverse Event Assessment	X	X	X	X	X	X	X	X	X	X	X	X	X	X
NRS pain assessments				X 	X 	X 	X 	X 	X	X				X
Subject home diary record (NRS)								X	X 	X 				X
Paper Diary (review, distribution and/or collection)								X 	X 	X 				X

Assessment	Screening	In Patient							Follow-Up				Unscheduled Visit	Early Termination
		Prior to Surgery	Surgery	Post-Surgery	24h	48h	72h	96h	8±1 days	15±2 days	29±2 days	36±2 days 		
Study Day	-45 to -1	0	0	0	1	2	3	4						
Subject home diary (analgesic consumption)								X	X 	X 				X
Dispense outpatient opioid rescue if needed								X 						
PGE assessment								X	X	X	X			X
IGE assessment								X	X	X	X			X
Blood draw for PK analysis		X		X 	X 									

1. Day 36 visit will occur if insufficient wound healing is assessed by the Investigator at the Day 29 visit.
2. Note pregnancy tests are for FCBP; urine pregnancy test is to be performed within 24 hours of scheduled surgery
3. Vital signs: 1, 2, 4, 6, 12, 24 and every 8 hours thereafter (if awake at time of assessment between the hours of 00:00 and 06:00) until discharge from the inpatient unit (may not miss two consecutive assessments). There will be a ±5-minute window allowed for the collection of vital signs in the first 4 hours after the end of surgery, after which will be a ±15-minute window allowed.
4. A complete medical history and physical examination including all major body systems will be performed at Screening. In addition, at the following times, an interim medical history and targeted physical examination will be performed prior to surgery (if not done on D-1), and to capture changes after Surgery, at 96 hours (within 4 hours of discharge), and Day 8, Day 15 and Day 29 after the administration of study medication or if the subject terminates early, at that time if allowed. Body weight (kg), in indoor clothing, but without shoes, will be measured at Screening, at 96 hours and Day 29, or at the time of discontinuation. Height (in cm) will be measured and BMI will be calculated at Screening only.
5. Post-Surgery ECG should be performed at 24 hours (±2 hours) after study medication administration
6. Surgical Site assessment: 96 hours (±4 hours) after study medication administration but prior to discharge from the inpatient unit
7. Neurosensory Exam of the Foot / Great toe (bilateral): 96 hours after study medication administration but within 4 hours of discharge from the inpatient unit
8. Clinical Laboratory tests (chemistry, hematology, and urinalysis) should be performed at screening (note if not done during screening, then perform prior to surgery) and prior to discharge from the inpatient unit (Lab collection window for 96h is ±30 min)
9. NRS pain assessments during the inpatient stay, at T0.5, 1, 2, 4, 6, 8, 12, 16, 20, 24, and every 4 hours (if awake at time of assessment and if no rescue opioid had been administered in the past 4 hours) until discharge from the inpatient unit. Pain scores may be skipped between the hours of midnight and 6 a.m., but the subject may not miss two consecutive assessments. An additional NRS assessment must be obtained 4 hours (±15 min) after every rescue dose even if this time point occurs between midnight and 6 a.m. The T12, T24, T48, T72 and T96h assessments must be completed even if the subject is asleep at these times. There will be a ±5-minute window allowed for the collection of each assessment in the first 4 hours after the end of surgery, after which will be a ±15-minute window allowed.
10. 2x/day through Day 15
11. Review Subject Diary instructions with subject
12. Dispense Subject Diary
13. Collect Subject Diary Data
14. Dispense no more than 6 tablets of oxycodone 5 mg tablets for use tid prn (although # tablets and refills per investigator discretion).
15. Collect blood samples if subject is participating in the PK study. The time points for collection are at baseline (before dosing), and at T5min, T10 min, T15min, T30min, T45min, and T1, T1.5, T2, T2.5, T3, T4, T6, T8, T12, T16, and T24h (a total of 17 samples). There will be a ±2-minute window allowed for the 5 to 15-minute collections, a ±5-minute window allowed for collections T30 min through T4h, and a ±15-minute window for collections after T4 hours.

